PROCOVAXED Trial Workflow on Intervention Blocks

Introduction to ED Staff: Clinical Research Coordinators (CRCs) will set up their workstation in the ED and introduce themselves to ED staff (nurses, physicians and mid-levels), informing them that they will be doing the PROCOVAXED study that day.

They will avoid telling providers intervention vs non-intervention arms.

Initial Screening and Scripted Consent for Surveys: CRCs will review ED dashboards for inclusion and exclusion information. When an eligible patient is identified, the CRC will ask the nurse or doctor caring for the patient whether it is Ok for them to approach the patient about the first survey. Whenever possible, the CRC will ask the provider to first ask the patient if they may speak to them.

For provider approved patients: CRCs will approach eligible patients and deliver a scripted consent for two short surveys (Pre-intervention) FIRST SURVEY and the (Post-Intervention) SECOND SURVEY. See Scripted Consent for the Intervention periods.

Complete PROCOVAXED Screening. Enrollment log for all patients.

First Survey in the ED: For patients agreeing to the above surveys, we will administer a short survey – a baseline survey to be complete after obtaining scripted consent at the beginning of their ED visit (before exposure to the messaging platform intervention – PROCOVAXED FIRST SURVEY). CRCs will have the option of inputting survey responses to REDCap on iPads in real time or using paper surveys (and later inputting into REDCap). **These surveys are to be delivered orally (CRC asks questions), not via handing them out.**

Covid Vaccine Flyer, Videos and Telling Provider to Deliver Message: At the end of the survey, the CRC will deliver the Covid vaccine information flyer and ask the patient if they will watch a short video about Covid vaccines. If they agree to watch the video, the CRC will show them the video on the iPad. After finishing with the video, the CRC will tell the subject that they will be back in about an hour for the second survey. The CRC will then leave the room and tell the patient's primary provider (doctor, mid-level practitioner, or nurse) to deliver the message (hand them the scripted message).

Intervention: The intervention will consist of three messaging platforms to reduce vaccine hesitancy that have been produced in Specific Aims I and II:

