The two primary outcomes are the verbal acceptance (Second Survey response) of a Covid vaccine in the ED and the receipt of at least one dose of a Covid vaccine dose within 30 to 32 days after the index ED visit. Both outcomes will be compared using mixed logistic regression with a fixed effect for randomization assignment, a random slope to allow for clustering by enrolling center, and a random slope to allow for secular trends. The treatment effect will be tested by the coefficient for the fixed effect of intervention along with 95% confidence intervals

- **Sub-analyses**

Another focus of this research is on the ED Usual Source of Care group, defined on the FIRST SURVEY questions as

- An answer of “No” or “Unsure” to the question: “*Do you have a regular clinic or doctor for medical care?*”

OR,

- *If they say “Yes” to the question: “Do you have a regular clinic or doctor for medical care?”, an answer of > 2 years to the question “If YES to regular doctor, when was the last time you saw this doctor or went to this clinic?”*

We will conduct subgroup analyses of the same primary outcomes of this ED Usual Source of Care group.

We will additionally stratify outcomes by study site (representing different regions of the country and different communities), age, gender, and race/ethnicity. We will also analyze outcomes according to patient-level experience characteristics, such as having already had COVID-19.

- **Rationale for time (1 week unit) cluster and consideration of Alternative Study Designs:**

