result in greater acceptance and uptake of the COVID-19 vaccine. Following the recommendations of Hussey and Hughes, our statistical analyses of AIMS III and IV will focus on comparing the vaccine and uptake rates during the time periods when PROCOVAXED is in place (intervention) and when the system is not in place (usual care) using mixed effects logistic models.^{122,123} The outcomes of interest are the binary indicators of whether a patient will accept the COVID-19 vaccine ("Will you accept the COVID-19 vaccine if it was offered to you" – yes/no) and whether they have received a COVID-19 vaccine (uptake - yes/no) upon follow-up. Models will include a random center effect to accommodate potential within-center characteristics (e.g., case mix, demographics), as well as terms for time and intervention. Hypothesis tests will focus on the statistical significance of the intervention indicator. We will fit the mixed effects models using maximum likelihood and routines in Stata or SAS.

We will test our primary hypothesis and analyze outcomes according to the study arm (index visit in intervention month vs non-intervention month) to which patients were allocated, regardless of whether they received PROCOVAXED messaging or not - **intention to treat analysis**. We will also conduct a **per-protocol analysis**, in which we assess results that would occur if they actually did or did not receive PROCOVAXED messaging (e.g., viewed the video clip given to them) during their index visit (ascertained by direct questioning in the Outcome Survey). When compared to the primary analysis, the per-protocol analysis will allow us to dissect the reasons for success (or failure) in demonstrating improved vaccine acceptance and uptake with PROCOVAXED. For example, if we find better acceptance and uptake in the per protocol analysis and not in the intention to treat allocation analysis, we would subsequently seek ways to improve delivery of PROCOVAXED messaging. Conversely, if both analyses fail to improve acceptance, then the PROCOVAXED intervention truly fails and other efforts to improve delivery would not be indicated. In addition to the effects on *total* vaccine acceptance, we will also examine the effect of PROCOVAXED on acceptance in patient sub-groups, especially African Americans and Latinos. PROCOVAXED may work for one patient sub-group and not others - these additional analyses will guide future directions and modifications of PROCOVAXED messaging.

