vaccination in ED USCARE patients. Considering the commonality of hesitancy (non-acceptance), the high benefit of increasing acceptance and the negligible risk of the intervention (a trusted messaging program), even a small effect size of increased acceptance would be a clinically important difference. By investigator consensus and in consultation with a panel of health policy experts, we have determined that PROCOVAXED would be clinically useful if it increased acceptance by 7%. Similarly, with the same considerations of negligible risk, we have determined that PROCOVAXED would be useful with an effect size on vaccine uptake of 7%. Our sample size calculations accommodate the randomization of clusters design consisting of 1 week periods (implementation of PROCOVAXED months and non-implementation) to the intervention at each of six sites. To avoid period effects, we will assign sites using a Latin square design S2. This design is more efficient than either the randomization of site for the study period or for individual subject randomization. We base the sample size calculation on the comparison of the proportion of patients who accept the vaccine between the PROCOVAXED and usual care time periods using standard formulae for individual randomization. We have verified that these sample sizes are conservative by simulation of data using a mixed random effects model. When our protocol was originally written in February 2021, vaccines were not widely available and the degree of baseline vaccine acceptance and uptake was unknown. We therefore calculated sample sizes for a wide range of vaccine acceptance and uptake rates with a plan to measure these in the non-intervention (control) group during the first month of the trial. After the first month, we estimate that our baseline vaccine acceptance and uptake rates (without intervention) will be approximately 15%. With this baseline uptake rate of 15%, we find that at an alpha=0.05 level and a power of at least 0.9, we will need to enroll 1,290 patients (645 in each arm) in the study to detect the difference of interest (a setting in which the vaccine acceptance rate will increase by 7% in PROCOVAXED weeks).

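### The per-protocol reading rules can take self-selection for poor delivery, or an inconclusive result for outright failure; the primary ITT test is unaffected

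*Combined protocol and SAP*

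**What the plan says.** All places are in the combined protocol and SAP. Under Data Analysis, the Statistical approach text makes ITT primary and adds a per-protocol analysis in which "we assess results that would occur if they actually did or did not receive PROCOVAXED messaging". Viewing the video is given as an example of receipt, and receipt is "ascertained by direct questioning in the Outcome Survey". The models described there have a random centre effect "as well as terms for time and intervention". No patient-level term appears there or under Primary Analysis, and no separate per-protocol model or comparator is given.

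Two readings follow. The first, offered as an example, is the case "if we find better acceptance and uptake in the per protocol analysis and not in the intention to treat allocation analysis", which leads to work on delivery. The second applies if both analyses fail on acceptance: "then the PROCOVAXED intervention truly fails and other efforts to improve delivery would not be indicated".

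Three other places bear on this:

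- Study Procedures: Intervention Blocks has the coordinator "ask the patient if they will watch a short video about Covid vaccines". Consents and Rationale confirms that the video is not played if the patient refuses.
- Data Recording and Entry has coordinators log whether each approached patient received the messaging platforms.
- Sample Size Considerations states that "we have determined that PROCOVAXED would be clinically useful if it increased acceptance by 7" per cent, and also regards even a small gain as clinically important.

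**The concern.** Agreeing to watch a vaccine video is plausibly related to willingness to be vaccinated. Viewers may therefore accept more often than control-week patients even if the video does nothing, because the control group still contains the people who would have refused it. The first rule would read that gap as evidence that the messaging works and only delivery is lacking.

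The second rule treats two non-positive results as proof of failure. Primary Analysis does provide an interval: "The treatment effect will be tested by the coefficient for the fixed effect of intervention along with 95% confidence intervals". But it is attached to a logistic coefficient, and neither rule refers to it.

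The plan gives this comparison the task of explaining why the trial succeeded or failed and of steering later work. What is at stake is that secondary interpretation.

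**Working it through.** **Inputs from Sample Size Considerations.** Control rate 15%, target 22%, alpha 0.05, power 0.9, 645 per arm. **Assumptions not in the documents.** Share viewing the video w = 70-90%; acceptance among refusers r = 5-10%; a threshold of z > 1.96 for a positive result; no clustering; acceptance only; receipt known without error.

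**Plan's own figure.** With mean proportion 0.185, n = [1.960√(2·0.185·0.815) + 1.282√(0.15·0.85 + 0.22·0.78)]² / 0.07² = (1.0763 + 0.7009)² / 0.0049 = 644.6, so 645 per arm and 1,290 in total. The figure reproduces with a two-sided test.

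**Rule 1, no true effect, intervention-week viewers against control-week patients.** The intervention arm as a whole accepts at 15%, so viewers accept at v = (0.15 − (1 − w)r)/w and the spurious gap is v − 0.15. For w = 0.7, r = 0.075: v = (0.15 − 0.0225)/0.7 = 0.182, a gap of 3.2 points. The last column is the share of 200,000 simulated trials (pooled z-tests) with a positive receipt contrast and an ITT result that is not.

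| Viewing share w | Refuser acceptance r | Spurious gap (points) | Rule 1 triggered |
|---|---|---|---|
| 0.9 | 10% | +0.6 | 2% |
| 0.9 | 5% | +1.1 | 5% |
| 0.7 | 10% | +2.1 | 13% |
| 0.7 | 7.5% | +3.2 | 27% |
| 0.7 | 5% | +4.3 | 44% |
| 0.7 or 0.9 | 15% (no selection) | 0 | 1.0% or 0.5% |

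The rule names acceptance and uptake. If both must be positive per protocol and neither on ITT, assuming equal rates for the two outcomes and a correlation of 0.3 to 0.7, the 27% falls to 10-15%, the 44% to 23-30%, and the 2% to under 0.5%.

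**Rule 2, full receipt.** The two analyses then coincide, and both miss a true gain d with probability 1 − Φ((d − 1.96·SE₀)/SE₁), where SE₀ is the pooled and SE₁ the unpooled standard error.

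- d = 0.04: (0.04 − 1.96·0.02092)/0.02089 = −0.05, so 52% are missed.
- d = 0.07: (0.07 − 1.96·0.02162)/0.02153 = 1.28, so 10% are missed.

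Full receipt is not the only case. If a true 4-point ITT gain acts through viewers only, both analyses fail in 30-45% of trials without selection (w = 0.7 to 0.9), 36% at w = 0.9, r = 10%, and 4% at w = 0.7, r = 7.5%. Selection makes this error rarer, because it pushes the per-protocol result upwards.

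**What a non-significant ITT result can leave open** (unpooled 95% CI, control 15%).

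- Observed +3.5 points: 3.5 ± 1.96·2.08, or −0.6 to +7.6. The 7-point target is not excluded.
- Observed +2.5 points: 2.5 ± 1.96·2.05, or −1.5 to +6.5. The target is excluded, but smaller gains are not.

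**The case against.** The case against has real force.

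- The first reading is introduced as an example, carries no threshold and decides nothing in the trial. ITT is primary. The percentages above depend on a 1.96 cut-off that the plan does not state.
- The video is one of three platforms. The flyer and the provider's script do not depend on agreeing to the video. If receipt means any platform, it may be near-universal and selection small. A provider who omits the script is a genuine delivery failure, which is what the first rule is meant to find.
- A reader might infer that the per-protocol analysis is planned without adjustment. The documents do not say so. Its model is unspecified, and the absence of patient-level terms is known only from the models described for the main comparison.
- A reader might infer that misreported receipt distorts the result. Nothing here shows that. The coordinator shows the video in person and receipt is logged, so self-report can be checked.
- A reader might want to declare no useful effect whenever the upper ITT limit is below 7 points. The plan does not support that, because it also values small gains; the +2.5-point example would be wrongly dismissed.

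These points limit the size and reach of the concern. They do not remove it: on the plan's own example of receipt, the first rule has no place for self-selection, and the second has no place for an inconclusive result.

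**Conclusion.** The point holds as a matter for consideration, confined to secondary interpretation. When receipt means viewing the video, self-selection alone can trigger the first rule in 2% to 44% of trials under the assumed ranges. It is less frequent if acceptance and uptake must agree, and small if receipt is near-universal. This range illustrates the mechanism and does not predict an error rate, since the viewing share and refuser acceptance are not in the documents. The second rule would call a real 4-point gain a failure in about 52% of trials and the 7-point design gain in about 10%, with full receipt and no clustering. Clustering that the design does not offset would raise these figures.

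A reader might infer that the trial's main conclusion is at risk. It is not: the primary ITT test and the sample size do not depend on either rule.

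**What to change.** 1. Replace the statement of outright failure with a conclusion from the ITT risk difference and its 95% CI. Report a non-significant result as no demonstrated effect, and state which gains remain compatible with the data. Describe an upper limit below 7 points only as excluding the gain the trial was designed to detect. Because the model is logistic, the interval must be converted to the risk-difference scale; for reference, 15% to 22% is an odds ratio of (0.22/0.78)/(0.15/0.85) = 1.60.
2. For the per-protocol analysis, define receipt platform by platform from the coordinators' log, with self-report as a check. Compare intervention-week receivers with control-week patients, adjust for first-survey covariates, and label the contrast observational with possible residual confounding, since adjustment cannot remove unmeasured motivation.
3. Reword the first rule so that self-selection stands beside poor delivery as an explanation.

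The cost is SAP wording and a little more secondary analysis on data already planned for collection. The secondary result may look less favourable.

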Second Survey in the ED: We will administer a second short survey at some time (approximately 1 hour) after the FIRST SURVEY. See SECOND SURVEY: NON-INTERVENTION GROUP. These second surveys in the non-intervention group have the same key primary and secondary outcome questions as in the INTERVENTION GROUP second surveys. SECOND SURVEY: NON-INTERVENTION GROUP.

NOTE: All of the above study procedures should be performed in patient waiting times and not interfere or disrupt patient care in any way.

- **Research Staff Informing of ED Providers when Participants will accept Covid vaccine**

At this time all of our EDs have the capability of administering COVID19 vaccines in some manner, and we expect that this will continue for at least the first 6 months of the trial. The last question in the SECOND SURVEY **in both arms** of the study is “Would you accept the Covid vaccine in the emergency department today if your doctor asked

you?" When a participant says they will accept the vaccine, the CRC or research staff will ask the patient if they can notify the patient's providers (nurse and/or physician) that they said they will accept the vaccine. They will also ask the patient if they (the CRC) can check to see if the patient receives the vaccine in the ED.

Other than this question and notification, research staff will not push that they get vaccinated.

- **Consent for 1- Month Follow Up Surveys for patients saying No to Vaccine in ED**

For all patients saying **no** to the question "*Would you accept the Covid vaccine in the emergency department today if your doctor asked you?*", research staff will ask if they can contact them and review their records in a month for follow up via full written consent. If patient says yes, then the CRC will get full **written** informed consent, including a separate HIPAA form, for review of their records and phone call. See FOLLOW UP Consent. Patients will not be compensated for participation. We will then ask Subjects for their best phone number(s) to reach them for a follow-up phone call. Sites will maintain a separate password protected database of subject IDs and follow up phone #s. Patients may agree to a phone call and not the EHR review, or vice versa. In those cases obtain the relevant consent, and note that they have accepted only one or the other.

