CRCs will review Master Data Flow daily (workdays) to determine which subjects have reached the 28-day follow-up time period. The CRC will conduct the first follow-up EHR review and, if necessary, follow up phone call attempt on that 28th index day. For the subsequent second and third EHR reviews and follow-up phone calls, CRCs will use the following weekday calendar, which will ensure no greater than 32 days between the index visit and final outcome ascertainment:

Index Study Visit Day of Week	First Call (Same day of week as index study visit – 4 weeks later)	Second Call	Third Call
Monday	Monday	Tuesday	Wednesday
Tuesday	Tuesday	Wednesday	Thursday
Wednesday	Wednesday	Thursday	Friday
Thursday	Thursday	Friday	Monday
Friday	Friday	Monday	Tuesday

Study subject's medical record #s and telephone #s will be accessed from the **PROCOVAXED Follow up sheet. The CRC who conducts this EHR and phone follow-up will be blinded to the subject's study group assignment (intervention vs non-intervention), i.e., a separate CRC who does not recruit at that site will conduct this phone follow-up.**

- The CRC will first review the EHR to determine whether there is any record of a Covid vaccination in the preceding time period from the study index visit. If there is a record of vaccination, the CRC will record what date and where the study received it. See **Follow up Data Collection** form.
- If there is no record of vaccination in the EHR, the CRC will proceed with a phone call to the study subject. See **Follow up Data Collection** form. CRCs will enter follow up data on both the Master Data Flow and Follow up spreadsheets

via REDCap links.

- If the patient does not answer the phone that morning, the CRC will place two more calls to the study subject over the next 2 workdays. They will vary the time of these calls to improve response.
- If the patient does not answer the phone by the third call, the CRC will leave a message with the phone # of the study team. No more calls will be initiated by the study team after this third call.
- If there is no call received from the study subject one week after the 3rd call, the phone follow up will be considered as incomplete.

Of note, CRCs will only review EHR and conduct phone follow-up with study subjects who have given written consent for these follow-up techniques.

In terms of final ascertainment of Specific Aim 4 (uptake of Covid Vaccine within 28 to 32 days of index ED visit), we will use the following scheme:

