	Any of the following:
Yes, Covid vaccine received	
• Confirmed receipt of Covid vaccine during index ED visit• Confirmed receipt of Covid vaccine via EHR review• Confirmed receipt of Covid vaccine via phone follow-up call

	
All of the following:
 
 • Did not receive Covid vaccine in ED during index visit • Did not receive Covid vaccine on EHR review • Did not receive Covid vaccine on phone follow-up call 
No, Covid vaccine not received
 
**If subject did not receive Covid vaccine in the ED, these 2 scenarios will also qualify as Covid vaccine not received:
 
 • Did not received Covid vaccine on EHR review but unable to complete phone follow-up • Did not received Covid vaccine on phone follow-up but unable to complete EHR review
Indeterminate	Unable to review EHR and Unable to contact subject via phone call

- **Data Recording and Entry**

CRCs will record survey responses and other data via two mechanisms:

- Direct entry into the PROCOVAXED Study REDCap database in real time during surveys via secure links
- Recording onto paper forms first. Then entry of survey information and data after each participant enrollment.

CRCs will keep a running log of all study flow and enrollment, recording on REDCap forms the following data for all patients approached: study date, study arm, “Yes” and “No” to having received a Covid vaccine, “Yes” and “No” agreeing to first surveys, delivery or non-receipt of messaging platforms, agreeing to receipt of study vaccines, receipt of vaccines in the ED, “Yes” and “No” agreeing to follow-up calls and EHR review. See Enrollment Log and Master Data Flow. CRCs will also record First and Second Survey responses on REDCap. Sites are allowed to use either one of two methods for REDCap data entry: recording of survey response on printed sheets and later entering on REDCap, or recording responses in real time directly on REDCap via iPads.

- **Data Analysis**
- **Primary Analysis**

We will compare primary outcomes in patients seen on PROCOVAXED intervention dates with those seen on non-intervention dates to test our 2 study hypotheses. We will measure outcomes in all ED patients surveyed as our group of primary outcome

analysis.

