With this same baseline 15% rate of uptake and the same specifications for power, we will need to enroll 1,290 patients (645 in each arm) to detect a vaccine uptake difference (the primary outcome of Specific Aim IV) of 7%. Thus, our target enrollment for this implementation trial is 1290 subjects across all sites.

In terms of total projected time for enrollment, we expect a minimum enrollment of 1 subject per site per day (6 hour block) at the 5 sites, or 25 enrollees per 5 day work week. We therefore expect to attain our target enrollment of 1290 subjects in approximately 50 weeks.

- **Consents and Rationale**

Survey Consent We will obtain scripted verbal consent for the surveys in the usual manner that we have conducted other survey studies of similar design and scope - (CHR. See 2 versions of this Scripted consent for the Intervention periods and for the Non-intervention periods. (Intervention and Non-Intervention).

We will obtain written consent for follow up chart review and phone calls. See FOLLOW UP Consent.

With regards to consent for delivery of the intervention (Covid vaccine

messaging) during intervention periods, we must emphasize that messaging for vaccine hesitancy is firmly a part of standard best-practice emergency department care (messaging of this type is currently be enacted in EDs across the US). Delivery of all of the vaccine messaging platforms is therefore an accepted common best practice not requiring consent. To add an extra layer of consent could even lead to greater vaccine hesitancy. We therefore plan the following processes with verbal assent during the PROCOVAXED FIRST SURVEY in intervention months:

- Handing patients the Covid vaccine message information sheet at the end of the first survey.
- Informing the patient's provider(s) of the short scripted vaccine message to deliver to the patient sometime after the FIRST SURVEY
- At the end of the FIRST SURVEY, asking patients if they are willing to watch the vaccine messaging video(s). If the patient says Yes, then we will play the video. If the patient says no, we will not play the video.

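### The 90% power stated for vaccine uptake assumes that every outcome is known: 1,290 is the bare individual-randomisation size, with no allowance for Indeterminate patients

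*Combined protocol and SAP*

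**What the plan says.** The Sample Size Considerations section compares acceptance proportions "using standard formulae for individual randomization", at a control rate of 15%, a gain of 7 points, alpha 0.05 and power of at least 0.9. It adds: "We have verified that these sample sizes are conservative by simulation of data using a mixed random effects model". No intraclass correlation, variance component or simulated power is given. The same section speaks of six sites, where the rest of the document has five. For uptake it repeats the number: "we will need to enroll 1,290 patients (645 in each arm) to detect a vaccine uptake difference", and makes 1,290 the enrolment target.

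Uptake is ascertained differently from acceptance. Patients vaccinated in the ED are confirmed there. For the rest, the follow-up section states that "CRCs will only review EHR and conduct phone follow-up with study subjects who have given written consent for these follow-up techniques". The consent is optional and can be partial: "Patients may agree to a phone call and not the EHR review, or vice versa". The ascertainment scheme accepts either route alone as enough for a No, and labels as Indeterminate those for whom staff were "Unable to review EHR and Unable to contact subject via phone call".

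The Primary Analysis section says "We will measure outcomes in all ED patients surveyed as our group of primary outcome" analysis, and "Both outcomes will be compared using mixed logistic regression with a fixed effect for randomization assignment". It does not say what happens to Indeterminates. The Statistical approach section describes the model as a random centre effect with time and intervention terms.

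**The concern.** A sample size that just reaches 0.90 with complete data has been carried over unchanged to an outcome that the protocol itself expects to be unknown for some patients. Acceptance is recorded at the second survey. Uptake, for most patients, needs a further signed consent and then a successful record review or call a month later.

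The stake is how a null uptake result would be read. The Statistical approach section is ready to conclude that the intervention has failed if both the intention-to-treat and per-protocol analyses show no gain; its wording there concerns acceptance. Applying the same reading to uptake would lean on a power that holds only with full ascertainment.

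**Working it through.** **Inputs from the documents.** Control 15%, intervention 22%, alpha 0.05, power 0.9, 645 per arm; 5 sites with 50 one-week blocks each. Two-sidedness is inferred, because only that version gives 1,290. Loss rate, share of the effect occurring in the ED, intraclass correlation (ICC), between-site variance and the rule for Indeterminates are not in the documents and are assumed below.

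**1. The plan's figure.** Pooled two-proportion formula, mean rate 0.185:

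n = [1.960 × √(2 × 0.185 × 0.815) + 1.2816 × √(0.15 × 0.85 + 0.22 × 0.78)]² / 0.07² = (1.0763 + 0.7009)² / 0.0049 = 644.56 per arm.

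Rounded up, this is 645, or 1,290 in total. Power is 0.9002 at 645 and 0.8998 at 644. Other versions do not match: unpooled 1,284, continuity-corrected 1,346, one-sided 1,052.

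**2. Patients who depend on follow-up consent.** The unvaccinated number 645 × 0.85 + 645 × 0.78 = 548.25 + 503.10 = 1,051, or 81.5% of 1,290. This is a lower bound, since patients vaccinated after the ED visit also need follow-up.

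**3. Uptake power with loss, no clustering.** Let p be true uptake and e the proportion vaccinated in the ED (2, 5 or 10% in control, plus a share f of the 7 points in intervention). Let L be the loss among the never-vaccinated and kL the loss among late vaccinees. Classified as vaccinated: V = e + (p − e)(1 − kL). Classified as unvaccinated: U = (1 − p)(1 − L). If Indeterminates are excluded, n = 645(V + U) and the rate is V/(V + U). If they count as No, n = 645 and the rate is V.

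Example with L = 20%, k = 1, f = 0, e = 5%: V = 0.130 versus 0.186. Counted as No, power is 0.788. Excluded, n = 645 × 0.81 = 522 per arm, rates are 0.1605 versus 0.2296, and power is 0.806.

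Example with k = 0: excluded, rates are 0.15/0.83 = 0.1807 versus 0.22/0.844 = 0.2607, and power is 0.887. Counted as No, nobody is misclassified and power stays 0.9002 at any loss.

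| 20% loss | Excluded | Counted as No |
|---|---|---|
| Uniform over all patients (benchmark) | 0.826 | 0.809 |
| Among those not vaccinated in the ED, k = 1, none of the effect in the ED | 0.79–0.82 | 0.77–0.80 |
| Same, half in the ED | 0.85–0.88 | 0.85–0.88 |
| Same, three quarters in the ED | 0.88–0.90 | 0.885–0.908 |
| Same, all in the ED | 0.90–0.92 | 0.91–0.93 |
| Late vaccinees lost at a quarter of the rate (k = 0.25), none in the ED | 0.867–0.873 | 0.874–0.880 |
| Only the unvaccinated lost (k = 0) | 0.887 | 0.900 |

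The values above 0.90 are not extra information. Loss there removes late vaccinations common to both arms. The 7.0-point difference then sits on lower rates (counted as No) or widens to 8.1–8.3 points (excluded).

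Uniform loss of 5, 10 and 30% gives 0.885, 0.868 and 0.774 excluded, and 0.881, 0.860 and 0.746 counted as No. Loss of 10 and 30% of the unvaccinated only, excluded, gives 0.8945 and 0.878.

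**4. Between-site gain.** If 5% of the variance lies between sites and the model removes it, 5% uniform loss (excluded) leaves 645 × 0.95/0.95 = 645 effective patients and power 0.900. At 20% loss it leaves 645 × 0.80/0.95 = 543 and power 0.845.

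**5. Acceptance.** Mean cluster size is 1,290/250 = 5.16 per site-week. With between-site variance share a, the design effect is 1 − a + 4.16 × ICC. For a from 0 to 5%, power is 0.888–0.903 at ICC 0.01, 0.876–0.891 at 0.02 and 0.839–0.854 at 0.05.

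A simulation of 5 sites × 50 weeks (control rate rising from 12% to 18%, beta-binomial site-weeks, Monte Carlo error about ±0.011) fitted centre and time terms only, with centres as fixed effects. It gave 0.901–0.905, 0.886–0.905 and 0.866–0.889, with type I error 0.057, 0.055 and 0.084. Adding a site-week random intercept gave 0.877–0.910, 0.870–0.890 and 0.837–0.865, with type I error 0.056, 0.054 and 0.051.

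**The case against.** The plan is open about its formula and says that a mixed-model simulation checked it. Each site serves as its own control across weeks, which can offset clustering. With centre and time terms only, acceptance power is about 0.90 at small ICC, so the plan's statement may well be right. That stands. A reader might infer from the individual-randomisation formula that acceptance is underpowered. The documents do not support this: a clear shortfall needs an ICC near 0.05, and no ICC is given.

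On uptake, the defence is that loss may cost little. ED vaccinees need no follow-up, one route suffices for the others, and follow-up consent is sought from patients who declined the vaccine or did not receive it in the ED. Loss may therefore fall mainly on the never-vaccinated, and counting Indeterminates as No then costs nothing. This also stands. It rules out the inference that uptake power must fall to about 0.77, or that it can hold near 0.90 only if most of the effect occurs in the ED. The 0.77 requires late vaccinees to be lost as often as the never-vaccinated, with none of the effect in the ED. The documents give no basis for that assumption or for its opposite.

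The defence does not supply the missing statements: the plan names no expected loss, no pattern of loss and no rule for Indeterminates. The 60-week calendar in the Randomization section is spare time, not a larger target.

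Nor does the mention of six sites show that the wrong design was simulated. Site count does not enter the formula, and the enrolment timeline uses five. It is a wording correction.

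**Conclusion.** The arithmetic is correct, and 1,290 need not be called wrong. What does not hold as written is an unqualified power of at least 0.9 for uptake: that is the figure with every outcome known, and there is no reserve behind it. With 20% loss and no clustering, power runs from 0.77 to 0.90 in most of the patterns examined. It exceeds 0.90 only where most or all of the effect occurs in the ED, for the reason given under the table. A between-site gain offsets a few per cent of loss, not 20%.

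For acceptance, the claim is unreported rather than refuted.

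Confidence is high for the arithmetic and for the dependence on consent. It is moderate for the size of the uptake shortfall, which rests on assumed loss rates and patterns.

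**What to change.** - Keep 1,290. State that 645 per arm gives 0.90 under individual randomisation with every outcome known.
- Restate uptake power over a stated range of Indeterminate share and loss pattern, including loss confined to the unvaccinated and loss shared with late vaccinees.
- Name one primary rule for Indeterminates (excluded, or counted as No) and make the other a sensitivity analysis.
- Report the simulated power for 5 sites × 50 one-week blocks under the planned model, with its ICC and between-site variance inputs and the type I error beside it. Retain the word conservative only if that supports it.
- Correct six sites to five. Reconcile the Sample Size statement that the design is more efficient than individual randomisation with the Rationale section, which credits individual randomisation with a smaller sample size.

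The cost is one simulation rerun, one stated rule, some wording and a less favourable stated power for uptake. No extra patients are needed.
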